9.2.2 Reactogenicity

Reactogenicity events are AEs that are common and known to occur following administration of this type of study vaccine. The following Toxicity Grading Scales will be used to grade solicited local (injection site) and systemic (subjective and quantitative) reactions:

Injection Site Reactogenicity Grading

Injection Site Reaction	Mild (Grade 1)	Moderate (Grade 2)	Severe (Grade 3)
Pain – experienced without touching the injection site (spontaneous discomfort)	Subject is aware of pain, but it does not interfere with daily activity, and no pain medication is taken	Subject is aware of pain; there is interference with daily activity or it requires repeated use of a non-narcotic pain reliever for >24 hours	Subject is aware of pain, and it prevents daily activity or requires any use of a narcotic pain reliever

Injection Site Reaction	Mild (Grade 1)	Moderate (Grade 2)	Severe (Grade 3)
Tenderness – hurts only when injection site is touched or the arm is moved	The area immediately surrounding the injection site hurts only when touched or with arm motion, and it does not interfere with daily activity	The area immediately surrounding the injection site hurts when touched or with arm motion, and it interferes with daily activity	The area immediately surrounding the injection site hurts when touched or with arm motion, and it prevents daily activity
Pruritus (Itching)	Does not interfere with daily activity activity		Prevents daily activity
Ecchymosis (Bruising)* Does not interfere with daily activity		Interferes with daily activity	Prevents daily activity
Erythema (Redness)* Does not interfere with daily activity		Interferes with daily activity	Prevents daily activity
Induration Does not interfere with (Hardness)/Swelling* daily activity		Interferes with daily activity	Prevents daily activity

^{*} Will also be measured in mm but size will not be used as halting criteria.

Ecchymosis, erythema, and induration/swelling as analyzed by measurement will be graded as follows:

Local (Injection Site) Reactogenicity Measurements

Local (Injection Site) Reaction	Small	Medium	Large
Ecchymosis (Bruising)*	<20 mm	20 mm – 50 mm	>50 mm
Erythema (Redness)*	<20 mm	20 mm – 50 mm	>50 mm
Induration (Hardness)/Swelling*	<20 mm	20 mm – 50 mm	>50 mm

^{*} Will not be used as halting criteria.

Subjective Systemic Reactogenicity Grading

Systemic (Subjective)	Mild (Grade 1)	Moderate (Grade 2)	Severe (Grade 3)
Feverishness (Chills/Shivering/Sweating)	No interference with daily activity	Some interference with daily activity	Significant interference, prevents daily activity

Systemic (Subjective)	Mild (Grade 1)	Moderate (Grade 2)	Severe (Grade 3)
Fatigue (Tiredness)	No interference with daily activity	Some interference with daily activity	Significant interference, prevents daily activity
Malaise (General Unwell Feeling)	No interference with daily activity	Some interference with daily activity	Significant interference, prevents daily activity
Myalgia (Body Aches/Muscular Pain)*	No interference with daily activity	Some interference with daily activity	Significant interference, prevents daily activity
Arthralgia (Joint Pain)*	No interference with daily activity	Some interference with daily activity	Significant interference, prevents daily activity
Headache	No interference with daily activity	Some interference with daily activity	Significant interference, prevents daily activity
Nausea No interference with daily activity		Some interference with daily activity	Significant interference, prevents daily activity

^{*} Not at injection site.

Oral temperature# will be graded as follows:

Quantitative Systemic Reactogenicity Grading

Systemic (Quantitative)	Mild (Grade 1)	Moderate (Grade 2)	Severe (Grade 3)
Envouk anali	38.0°C – 38.4°C	38.5°C – 38.9°C	>38.9°C
Fever* - oral [†]	100.4°F – 101.1°F	101.2°F – 102.0°F	>102.0°F

[#] Oral temperature assessed on Day 1 prior to the first study vaccination will be considered as baseline.

9.2.3 Additional Adverse Event Severity Grading

For Individuals 19-64 years of age, pulse and blood pressure[#] will be graded as follows:

Physiologic Parameter	Mild (Grade 1)	Moderate (Grade 2)	Severe (Grade 3)
Bradycardia - beats per minute	45 – 46	40 – 44	<40

^{*} A fever can be considered not related to the study product if an alternative etiology can be documented.

[†] Subjects must not eat or drink anything hot or cold, or smoke within 10 minutes prior to taking oral temperature.

Tachycardia - beats per minute	101 – 130	131 – 155	>155
Hypotension (systolic) mmHg	80 – 84	75 – 79	<75
Hypotension (diastolic) mmHg	50 – 54	45 – 49	<45
Hypertension (systolic) mmHg	151 – 155	156 – 160	>160
Hypertension (diastolic) mmHg	96 – 100	101 – 105	>105

[#] Pulse and blood pressure assessed on Day 1 prior to the first study vaccination will be considered as baseline.

For Individuals >65 years of age, pulse and blood pressure[#] will be graded as follows:

Physiologic Parameter	Mild (Grade 1)	Moderate (Grade 2)	Severe (Grade 3)
Bradycardia - beats per minute	45 – 46	40 – 44	<40
Tachycardia - beats per minute	101 – 130	131 – 155	>155
Hypotension (systolic) mm Hg	80 – 84	75 – 79	<75
Hypotension (diastolic) mm Hg	50 – 54	45 – 49	<45
Hypertension (systolic) mm Hg	161 – 165	166 – 170	>170
Hypertension (diastolic) mm Hg	96 – 100	101 – 105	>105

[#] Pulse and blood pressure assessed on Day 1 prior to the first study vaccination will be considered as baseline.

Clinical safety laboratory results[#] will be graded as follows:

Clinical Safety Laboratory Adverse Event Grading

Hematology	Mild (Grade 1)	Moderate (Grade 2)	Severe (Grade 3)
WBC 10 ³ /μL (Decrease)	2.5 - 3.9	1.5 - 2.4	<1.5
WBC 10 ³ /μL (Increase)	10.6 – 15.0	15.1 - 20.0	>20.0
Hgb g/dL (Decrease) (Female)	10.1 - 11.4	8.5 – 10	<8.5
Hgb g/dL (Decrease) (Male)	11.0 – 12.4	9.5 – 10.9	<9.5
Platelets 10 ³ /μL (Decrease)	125 – 139	100 – 124	<100
Platelets 10 ³ /μL (Increase)	416 – 550	551-750	>750

Chemistry	Mild (Grade 1)	Moderate (Grade 2)	Severe (Grade 3)
ALT IU/L (Increase) (Female)	44 – 100	101 - 200	>200
ALT IU/L (Increase) (Male)	61 – 138	139 – 275	>275
Total Bilirubin mg/dL (Increase) – when accompanied by any increase in ALT	1.30 – 1.59	1.60 – 1.80	>1.80
Total Bilirubin mg/dL (Increase) – when ALT is normal	1.30 – 1.89	1.90 – 2.40	>2.40
Creatinine mg/dL (Increase) (Female)	1.1 – 1.7	1.8 – 2.0	>2.0
Creatinine mg/dL (Increase) (Male)	1.4 – 1.7	1.8 - 2.0	>2.0

[#] Clinical laboratory evaluations assessed on Day 1 prior to the first study vaccination will be considered as baseline.

9.2.4 Serious Adverse Events

Serious Adverse Event (SAE): An AE or suspected adverse reaction is considered "serious" if, in the view of either the site principal investigator or sponsor, it results in any of the following outcomes:

- Death,
- A life-threatening AE*,
- Inpatient hospitalization or prolongation of existing hospitalization,

- A persistent or significant incapacity or substantial disruption of the ability to conduct normal life functions, or
- A congenital anomaly/birth defect.
- Important medical events that may not result in death, be life-threatening, or require hospitalizations may be considered serious when, based upon appropriate medical judgment they may jeopardize the patient or subject and may require medical or surgical intervention to prevent one of the outcomes listed in this definition. Examples of such medical events include allergic bronchospasm requiring intensive treatment in an emergency room or at home, blood dyscrasias or convulsions that do not result in inpatient hospitalization, or the development of drug dependency or drug abuse.
- * Life-threatening AE. An AE is considered "life-threatening" if, in the view of either the site principal investigator or sponsor, its occurrence places the patient or subject at immediate risk of death. It does not include an AE that, had it occurred in a more severe form, might have caused death.

SAEs will be:

- Assessed for severity and relationship to study product and alternate etiology (if not related to study product) by a licensed study physician listed on the Form FDA 1572 as the site principal investigator or sub-investigator.
- Recorded on the appropriate SAE form and eCRF.
- Followed through resolution by a licensed study physician listed on the Form FDA 1572 as the site principal investigator or sub-investigator.
- Reviewed and evaluated by an Independent Safety Monitor (ISM) (as deemed necessary), the DSMB (periodic review unless related), DMID, and the IRB.

9.2.5 Procedures to be Followed in the Event of Abnormal Laboratory Test Values or Abnormal Clinical Findings

The site principal investigator or appropriate sub-investigator is responsible for recording all AE/SAEs that are observed or reported during this trial, regardless of the relationship to study product. AE/SAEs, abnormal laboratory test values, or abnormal clinical findings will be collected, assessed, documented, reported, and followed appropriately, using a local laboratory as necessary. In determining eligibility, refer to section 5.2.3 and the protocol-specific MOP.

9.3 Reporting Procedures

Solicited injection site and systemic reactogenicity events will be documented and reported from the time of each study vaccination through 7 days after each study vaccination.

[figure not shown]
Clinical safety laboratory AEs will be documented and reported from the time of each study vaccination through approximately 7 days after each study vaccination.

Unsolicited non-serious AEs will be documented and reported from the time of each study vaccination through approximately 21 days after each study vaccination.

SAEs, MAAEs, including NOCMCs, and PIMMCs will be documented and reported from the time of the first study vaccination through approximately 12 months after the last study vaccination.

9.3.1 Serious Adverse Events

Any AE that meets a protocol-defined serious criterion must be submitted immediately (within 24 hours of site awareness) on an SAE form to the DMID Pharmacovigilance Group at the following address:

In addition to the SAE form, selected SAE data fields must also be entered into AdvantageEDCSM. Please see the protocol-specific MOP for details regarding this procedure.

Other supporting documentation of the event may be requested by the DMID Pharmacovigilance Group and should be provided as soon as possible.

The site will send a copy of the SAE report(s) to the ISM (as deemed necessary) when they are provided to the DMID Pharmacovigilance Group. The DMID Medical Monitor and DMID Clinical Project Manager will be notified of the SAE by the DMID Pharmacovigilance Group. The DMID Medical Monitor will review and assess the SAE for regulatory reporting and potential impact on study subject safety and protocol conduct.

At any time after completion of this trial, if the site principal investigator or appropriate sub-investigator becomes aware of an SAE that is suspected to be related to study product, the site principal investigator or appropriate sub-investigator will report the event to the DMID Pharmacovigilance Group.

9.3.2 Regulatory Reporting for Studies Conducted Under DMID-Sponsored IND

Following notification from the site principal investigator or appropriate sub-investigator, DMID, the Investigational New Drug (IND) sponsor, will report any suspected adverse reaction that is both serious and unexpected. DMID will report an AE as a suspected adverse reaction only if there is evidence to suggest a causal relationship between the drug and the AE. DMID will notify FDA and all participating site principal investigators (i.e., all principal investigators to whom the sponsor is providing drug under its IND(s) or under any principal investigator's IND(s)) in an IND safety report of potential serious risks from clinical trials or any other source, as soon as possible, but in no case later than 15 calendar days after the sponsor determines that the information qualifies for reporting as specified in 21 CFR Part 312.32. DMID will also notify FDA of any unexpected fatal or life-threatening suspected adverse reaction as soon as possible, but in no case later than 7 calendar days after the sponsor's initial receipt of the information. Relevant follow up information to an IND safety report will be submitted as soon as the information is available. Upon request from FDA, DMID will submit to FDA any additional data or information that the agency deems necessary, as soon as possible, but in no case later than 15 calendar days after receiving the request.

All serious events designated as "not related" to study product(s), will be reported to the FDA at least annually in a summary format.

9.3.3 Reporting of Pregnancy

Pregnancies occurring in study subjects will be reported via AdvantageEDCSM on the Pregnancy Report form. No further study vaccinations will be administered to pregnant subjects, but with the subject's permission all protocol-required venous blood samples will be obtained and the subject will continue to be followed for safety for the duration of this trial. Efforts will be made to follow all pregnancies reported during the course of this trial to pregnancy outcome pending the subject's permission.

9.4 Type and Duration of Follow-up of Subjects after Adverse Events

AEs will be collected, assessed, and followed through resolution from the time of each study vaccination through approximately 21 days after each study vaccination.

SAEs, MAAEs, including NOCMCs, and PIMMCs will be collected, assessed, and followed from the time of the first study vaccination through resolution even if this extends beyond the trial-reporting period (approximately 12 months after the last study vaccination).

Resolution of an AE/SAE is defined as the return to pretreatment status or stabilization of the condition with the expectation that it will remain chronic.

Follow-up procedures, evaluations, and outcomes will be recorded on the appropriate data collection form.

9.5 Halting Rules

Further enrollment and study vaccinations will be halted for DSMB review/recommendation if any of the following are reported:

- Any subject experiences ulceration, abscess, or necrosis at the injection site related to study product administration.
- Any 2 or more subjects experience laryngospasm, bronchospasm, or anaphylaxis within 1 day after administration of study product that is considered related to study product.
- Three or more subjects experience generalized urticaria (defined as occurring at more than two body parts) within 3 days after administration of study product that is considered related to study product.
- Any subject experiences a study vaccine-related SAE from the time of the first study vaccination through the subject's last study visit.
- Any subject experiences acute weakness of limbs and/or cranial nerve innervated muscles (description of potential signal of GBS) after administration of study product.
- Any subject develops a PIMMC after administration of study product.

This trial will also be halted for DSMB review/recommendation if, within 7 days after administration of either study vaccination, any of the following occurs within the AS03-adjuvanted treatment arms or within the two unadjuvanted treatment arms.

• 7% or more of subjects (with a minimum of 3 subjects) who received at least one dose of study vaccine to date, cumulative to both vaccine administration, across all groups, experience the same severe (Grade 3) study vaccine-related injection site reaction.

Ecchymosis, erythema, and induration/swelling will also be measured in mm but size will not be used as halting criteria.

- 7% or more of subjects (with a minimum of 3 subjects) who received at least one dose of study vaccine to date, cumulative to both vaccine administration, across all groups, experience the same severe (Grade 3) study vaccine-related subjective systemic reaction, for which the severity (grade) is corroborated by study personnel.
- 7% or more of subjects (with a minimum of 3 subjects) who received at least one dose of study vaccine to date, cumulative to both vaccine administration, across all groups, experience the same severe (Grade 3) study vaccine-related quantitative systemic reaction.
- 7% or more of subjects (with a minimum of 3 subjects) who received at least one dose of study vaccine to date, cumulative to both vaccine administration, across all groups, experience the same severe (Grade 3) study vaccine-related clinical safety laboratory AE.

Grading scales for solicited injection site and systemic (subjective and quantitative) reactions are included in Section 9.2.2.

Grading scales for clinical safety laboratory AEs are included in Section 9.2.3.

If any of the halting rules are met following any subject receipt of any study vaccination, then this trial will not continue with the remaining enrollments or study vaccinations without a review by and recommendation from the DSMB to proceed.

DMID retains the authority to suspend additional enrollment and study interventions/administration of study product during the entire trial, as applicable.

The DMID Medical Monitor is empowered to stop enrollment and study vaccinations if AEs that meet the halting criteria are reported.

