3.2 Study Outcome Measures

3.2.1 Primary

Safety:

- Occurrence of study vaccine-related serious adverse events (SAEs) from the time of the first study vaccination through approximately 12 months after the last study vaccination.
- Occurrence of solicited injection site and systemic reactogenicity events from the time of each study vaccination through 7 days after each study vaccination.
- Occurrence of clinical safety laboratory adverse events from the time of each study vaccination through approximately 7 days after each study vaccination.

Immunogenicity:

• For HAI and Neut antibodies, percentage of subjects achieving seroconversion against the influenza 2017 H7N9 study vaccine strain (defined as either a pre-vaccination titer <1:10 and a post-vaccination titer ≥1:40 or a pre-vaccination titer ≥1:10 and a minimum

- four-fold rise in post-vaccination titer) at approximately 21 days after the second study vaccination (Study Day 43).
- For HAI and Neut antibodies, percentage of subjects achieving titer ≥1:40 against the influenza 2017 H7N9 study vaccine strain at approximately 21 days after the second study vaccination (Study Day 43).
- Geometric Mean Titers (GMTs) of serum HAI and Neut antibodies against the influenza 2017 H7N9 vaccine strain at approximately 21 days after the second study vaccination (Study Day 43).

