8.2 Follow-up Visits

Follow-up visits are scheduled in reference to study vaccination dates as indicated for each visit window.

8.2.1 Visit 02, Day 4, Memory Aid Review, Phone Call (Window: Day 4±1 day post first study vaccination)

Study personnel will contact subjects by phone to solicit any AE/SAE, medical history, and concomitant medication information (including solicitation for receipt of any non-study influenza vaccines, including those that are experimental, what type (inactivated or live attenuated), what subtype (e.g., A/H3, A/H5, A/H9) and approximate date of vaccination will be recorded on the appropriate DCF, if known and not previously collected.) and review information on their memory aid. Based on the information, subjects may be asked to return to the clinic for evaluation.

8.2.2 Visit 03, Day 8, Clinic Visit (Window: Day 8+2 days post first study vaccination)

- Interim medical history, including an assessment for new medical conditions, stability of chronic diseases, and symptoms suggestive of PIMMCs, will be obtained by interview of subjects and any changes since the previous clinic visit or contact will be noted.
- Memory aid information will be reviewed with subjects.
- All concomitant medications (including solicitation for receipt of any non-study influenza vaccines, including those that are experimental, what type (inactivated or live attenuated), what subtype (e.g., A/H3, A/H5, A/H9) and approximate date of vaccination will be recorded on the appropriate DCF, if known and not previously collected.) will be recorded on the appropriate data collection form.
- All AE/SAEs will be recorded on the appropriate data collection form.
- A targeted physical examination, including an assessment for signs suggestive of PIMMCs, may be performed, if indicated based on review of interim medical history, by a study clinician licensed to make medical diagnoses and listed on the Form FDA 1572 as the site principal investigator or sub-investigator.
- The first study vaccination site will be examined.
- Approximately 10 mL of venous blood will be collected for safety labs, WBC, Hgb, PLT, ALT, T. Bili, Cr, and performed by the central (clinical) laboratory.
- Approximately 10 mL of venous blood will be collected for serum antibody assays.

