- Subjects will be provided with a memory aid and other study-related materials to record daily oral temperature, solicited injection site and systemic reactions, any unsolicited AEs, and concomitant medications. Subjects will be encouraged to take their oral temperature around the same time each day. Subjects must not eat or drink anything hot or cold, or smoke within 10 minutes prior to taking oral temperature. Subjects will be instructed on how to use their memory aid and how to measure and record AEs prior to discharge from the clinic. Subjects will be instructed to notify the study center if they develop any severe reactions after the second study vaccination. If the site principal investigator or appropriate sub-investigator deems the reaction severe enough, further instructions will be given to the subject on the proper course of action, including a return to the clinic for immediate evaluation if appropriate.

8.2.4 Visit 05, Day 25, Memory Aid Review, Phone Call (Window: Day 4±1 day post second study vaccination)

Study personnel will contact subjects by phone to solicit any AE/SAE, medical history, and concomitant medication information (including solicitation for receipt of any non-study influenza vaccines, including those that are experimental, what type (inactivated or live attenuated), what subtype (e.g., A/H3, A/H5, A/H9) and approximate date of vaccination will be recorded on the appropriate DCF, if known and not previously collected.) and review information on their memory aid. Based on the information, subjects may be asked to return to the clinic for evaluation. Note: For subjects who are discontinued from the receipt of the second study vaccination, AEs will be limited to SAEs, MAAEs, including NOCMCs, and PIMMCs.

8.2.5 Visit 06, Day 29, Clinic Visit (Window: Day 8+2 days post second study vaccination)

- Interim medical history, including an assessment for new medical conditions, stability of chronic diseases, and symptoms suggestive of PIMMCs, will be obtained by interview of subjects and any changes since the previous clinic visit or contact will be noted.
- Memory aid information will be reviewed with subjects.

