9.6.2 Data and Safety Monitoring Board (DSMB)

Safety oversight will be conducted by a DSMB that is an independent group of experts that monitors subject safety and advises DMID. The DSMB members will be separate and independent of study personnel participating in this trial and should not have scientific, financial or other conflict of interest related to this trial. The DSMB will consist of members with appropriate expertise to contribute to the interpretation of the data from this trial. The DSMB will operate under the rules of a DMID-approved charter that will be written at the organizational meeting of the DSMB. Procedures for DSMB reviews/meetings will be defined in the charter. Reports may include enrollment and demographic information, medical history, concomitant medications, physical assessments, clinical laboratory values, dosing compliance, and solicited and unsolicited AE/SAEs, HAI and Neut antibody assay results. The DSMB will review SAEs on a regular basis and ad hoc during this trial. The DMID Medical Monitor and the ISM (as deemed necessary) will be responsible for reviewing SAEs in real time.

The DSMB will conduct the following reviews:

- Bi-monthly safety data reviews (including monthly safety data and cumulative safety data) until the last subject completes the visit that occurs approximately 21 days after the last study vaccination.
- Interim analysis of serum antibody responses comparing venous blood samples collected at baseline, Visit 03, Visit 06, and Visit 07 for 25 subjects per adjuvanted treatment arm and 13 subjects per unadjuvanted treatment arm within the 19-64year-old stratum, and the first 15 subjects per adjuvanted treatment arm and 8 subjects per unadjuvanted treatment arm within the ≥65 year-old stratum. These reviews may be conducted as part of the scheduled monthly reviews or as the data become available. Reports will include data summarized by unblinded treatment arm, but the presentation will be in a format that prevents inadvertent unblinding of any individual subjects.
- Data review 9 days after all subjects have received Dose 2 (complete study visit number V06). This review may be conducted as part of the scheduled monthly reviews.
- Ad hoc when a halting rule is met or DMID/DSMB chair may convene an ad hoc meeting if there are immediate concerns regarding observations during the course of this trial.

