6.3.3. Per Protocol Population

The per protocol (PP) population includes all subjects in the mITT subset with the following exclusions:

- Data from all available visits for subjects found to be ineligible at baseline due to eligibility criteria that would impact immune response.
- Data from all visits subsequent to major protocol deviations, such as:
 - o Second study vaccination not received,
 - o Second study vaccination received out of window,
 - Receipt of non-study licensed live vaccine within 30 days before or after each study vaccination,
 - Receipt of non-study licensed inactivated vaccine within 14 days before or after each study vaccination,
 - Receipt of immunosuppressive therapy (e.g., corticosteroids) within 30 days before or after each study vaccination.
- Data from any visit that occurs out of window by more than one day:
 - O Visit 3 data collected before 6 days or after 10 days post first study vaccination
 - o Visit 4 data collected before 20 days or after 29 days post first study vaccination.
 - o Visit 6 data collected before 6 days or after 10 days post second study vaccination.
 - o For subjects who did not receive the second study vaccination, visit 6 data collected before 27 days or after 31 days post first study vaccination.
 - o Visit 7 data collected before 20 days or after 29 days post second study vaccination.
 - o For subjects who did not receive the second study vaccination, visit 7 data collected before 41 days or after 50 days post first study vaccination.
 - Visit 10 data collected before 165 days or after 195 days post second study vaccination.
 - o For subjects who did not receive the second study vaccination, visit 10 data collected before 200 days or after 216 days post first study vaccination.

For analyses using the PP population, subjects will be grouped based on study vaccinations received.

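### The Grade 3 laboratory halting rule ends 7 days after a dose, but the scheduled safety draws may fall 7, 8 or 9 days after it

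*Protocol*

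**What the plan says.** Protocol 9.5 lists four percentage criteria that halt the trial for DSMB review. Each needs at least 7% of subjects dosed so far, and at least three subjects. One lead-in governs all four: they count if, "within 7 days after administration of either study vaccination, any of the following occurs". The fourth criterion concerns subjects who "experience the same severe (Grade 3) study vaccine-related clinical safety laboratory AE".

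The routine safety draws after each dose are at Visit 03 (Protocol 8.2.2, "Window: Day 8+2 days post first study vaccination") and Visit 06 (8.2.5, "Window: Day 8+2 days post second study vaccination"). Protocol Appendix A and SAP Table 2 give the same windows. Protocol Table 2 alone shows Visit 06 as Day 8 plus or minus 3 days.

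Elsewhere the period for laboratory events is looser. Protocol 3.2.1 defines the endpoint as "Occurrence of clinical safety laboratory adverse events from the time of each study vaccination through approximately 7 days after each study vaccination", and the reporting text in 9.3 uses the same approximate period.

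**The concern.** A 7-day limit suits solicited reactions, which subjects record daily for 7 days. A laboratory abnormality is seen only when blood is drawn, and under the Day 8+2 window no routine post-dose draw comes before day 7. The laboratory criterion therefore meets its scheduled data only on the last day it covers.

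Read literally, a related Grade 3 result from a compliant draw on Day 9 or Day 10 is left out of the numerator, while that subject remains in the denominator. Two identical results would be treated differently because of appointment scheduling. Protocol 9.5 also ties the Medical Monitor's power to stop dosing to events that meet the halting criteria, so that power inherits the gap. The vaccine had not been given to humans before (Protocol 2.3.1), so the automatic stop should match its own data schedule.

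**Working it through.** **Day numbering.** Elapsed days = study day − 1, because the dose is on Day 1. The SAP's own figure checks this: Day 22+7 gives 21 to 28 days, as stated in SAP 4.4.5.

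**Draw window.** Day 8+2 is Days 8, 9 and 10, that is 7, 8 and 9 days after the dose. SAP 6.3.3 agrees. It excludes data more than one day out of window, and its Visit 3 limit is "Visit 3 data collected before 6 days or after 10 days post first study vaccination", which is 7 to 9 days widened by one day each side. The 7-day limit covers one of the three permitted days. Under Protocol Table 2's version of Visit 06 the permitted days are 4 to 10, and days 8, 9 and 10 still fall outside.

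**Assumptions for size.** Let f be the share of draws taken on Day 8, and r the per-dose probability of the same related Grade 3 laboratory event. The documents give neither. Doses are taken as independent, events are dated by the draw, and there is no dropout. The pools follow the 9.5 lead-in at planned enrolment: three AS03 arms of 160 (N = 480) and two unadjuvanted arms of 80 (N = 160). The thresholds are 0.07 × 160 = 11.2, so 12 subjects, and 0.07 × 480 = 33.6, so 34.

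**Rate needed to reach a counted 7%.** With one draw per subject the true rate needed is 7%/f: 7.8% at f = 0.9, 10% at 0.7, 14% at 0.5. With two draws the per-dose rate is r = (1 − √0.93)/f = 0.0356/f: 3.6% at f = 1, 4.0% at 0.9, 5.1% at 0.7, 7.1% at 0.5.

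**Single look at the end.** A subject is counted with probability q = 1 − (1 − rf)². The chance of reaching the threshold is the binomial upper tail. At r = 5%:

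| Pool | f = 1 | 0.9 | 0.7 | 0.5 |
|---|---|---|---|---|
| N = 160, ≥12 | 0.865 | 0.758 | 0.421 | 0.099 |
| N = 480, ≥34 | 0.983 | 0.924 | 0.455 | 0.024 |

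**Daily cumulative checks.** This simulation used 4,000 runs per cell, uniform accrual over 84 days and dose 2 at 21 days. Draws fell at 7 days with probability f and otherwise at 8 or 9. The rule was met on any day with at least 3 counted subjects making up at least 7% of those dosed to date.

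| Pool, r | All draws counted | f = 0.9 | 0.7 | 0.5 |
|---|---|---|---|---|
| N = 160, 4% | 0.66 | 0.54 | 0.26 | 0.06 |
| N = 160, 5% | 0.90 | 0.80 | 0.50 | 0.17 |
| N = 480, 4% | 0.77 | 0.54 | 0.09 | 0.00 |
| N = 480, 5% | 0.98 | 0.93 | 0.47 | 0.03 |

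**Away from the threshold.** At r = 2%, counting all draws against f = 0.7 gives about 8% against 1–2% (N = 160), and under 1% for both at N = 480. At r = 8% it gives over 99% against about 95% (N = 160), and over 99% for both at N = 480. At r = 10% and f = 0.5, rf = 5%, so the rule is met about 90% and 98% of the time.

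**The case against.** The strongest reply is that 9.5 asks when an event occurs, and no section says that a laboratory event begins on the day of the draw. Protocol 9.2.1 records onset dates, so an abnormality found on day 8 or 9 could be taken to have begun earlier. The surrounding text favours an inclusive reading: laboratory events are collected for approximately 7 days, Visits 03 and 06 are the draws that fit that description, and nothing tells anyone to discard a late one. A dropped qualifier in a shared lead-in is a likely explanation. This makes the exclusion conditional, but it does not settle how 9.5 should be applied, and two programmers could produce different counts.

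It is also fair that f and the 5% rate are assumptions, and that 5% sits close to the 3.6% break-even rate, where the loss is greatest. There is no evidence that f is as low as 0.5.

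Other safeguards reduce the harm. A halt leads to DSMB review and does not itself end the trial. The DSMB sees laboratory values at its regular reviews and again once Visit 06 is complete, unscheduled draws are allowed, and DMID may suspend dosing at any time. A Grade 3 value that does not fall to Grade 2 or less bars that subject's second dose. These are discretionary, periodic or limited to one subject, and none makes the automatic rule count the omitted draws. No endpoint or planned estimate is affected.

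**Conclusion.** The concern holds. As written, the laboratory halting criterion covers one of the three days on which its scheduled draws may be taken, provided a laboratory event is dated by its draw. The day arithmetic is certain. The size is not, because it depends on f and on the event rate. The cost is nil if every draw is on Day 8, substantial when the per-dose rate is near 4–5% and f is about 0.7 or lower, and small at f of 0.7 or more once rates are well above or below the threshold. This should be fixed: a safety rule should not depend on which permitted day a subject attends.

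**What to change.** In Protocol 9.5, separate the laboratory criterion from the shared lead-in. State that it counts all related Grade 3 results from the scheduled Visit 03 and Visit 06 draws, through Day 10 (9 days after each dose), and from any unscheduled draw in that period. Leave the 7-day limit for solicited reactions as it is. Naming the draws also removes the need for an onset rule.

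The cost is one clause and the matching change to the DSMB report programming, with no added visits or blood. As a separate clerical correction, change the Visit 06 window in Protocol Table 2 from plus or minus 3 days to +2 days, so that it agrees with 8.2.5 and Appendix A.
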